*\*Note:* [name], our community research associate, will provide the training and fidelity monitoring of our community partners. She has been involved in statewide coordination of evidence-based health promotion programs for older adults in Wisconsin for over 9 years. Part of her responsibilities have included training, overseeing, and fidelity monitoring for health promotion programs (e.g., the “Chronic Disease Self-Management” program). In addition, [name] (co-investigator) has expertise in developing tools for fidelity monitoring for the health promotion program “Stepping On.” These fidelity tools are used nationally to ensure high fidelity with dissemination of falls prevention programs. Treatment fidelity implementation in the proposed study is consistent with NIH Behavior Change Consortium Treatment Fidelity Workgroup recommendations involving study design, training of providers, delivery of treatment, receipt of treatment, and enactment of treatment skills.

**Wait-List Control Group:** Older adults assigned to the control group will be instructed to go about their daily routines during the first 12 weeks of the study. They will complete, in the same manner as the intervention group, assessments at baseline, 4, and 12 weeks. The control participants will receive the *Stand Up & Move More* intervention after 12 weeks.

**Measures:** Data collection sessions will be held the week prior to beginning the intervention (at the introductory meeting), at 4 weeks (following the delivery of the intervention), and at 12 weeks (follow-up) at readily accessible sites in each county (see Appendices for a summary table of outcomes assessment). Assessments will be completed by assessors trained by [name]. The assessors will be blinded to group assignment, and every effort will be made to ensure the assessors remain blinded throughout the duration of the study.

**Sedentary behavior** will be assessed both subjectively and objectively: **(a)** Participants will be interviewed by the investigators about their time spent sitting during the day in different activities (e.g., watching TV, reading) over the past week using a previously validated questionnaire for older adults; **(b)** Activity Monitors will be worn at each assessment for one week: The *activPAL*

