Adverse Event and Serious Adverse Event Collection and Reporting: Adverse events are not expected to occur. The health program facilitators will, however, at the beginning of each workshop session, distribute a brief questionnaire asking about any adverse events (e.g., falling while standing up, injury, muscle soreness, and/or increases in pain) that may have occurred during the previous week. Other information to be gathered at the beginning of each session includes whether any of the participants were sick or sought healthcare during the past week. The health program facilitators will review the responses and then follow-up with respondents during the break or at the end of the session. (Note: the health program facilitators will be trained by [name] to assess adverse events as part of a day-long ‘Stand Up and Move More’ workshop training session for the community partners). Adverse events (AE) occurring during the study will be documented and reported (to the DSMB, IRB, and NIA) by the Principal Investigator (PI). The occurrence of AEs will be assessed on an ongoing basis during the intervention. If patterns of recurrent AEs across participants suggest modifications of the study protocol are required, such changes will be implemented in consultation with NIH staff and the IRB of record. The PI will be responsible for ensuring participant safety on a daily basis. The PI or research assistant will call the health program facilitators on a weekly basis during the workshop to discuss safety concerns and delivery of intervention content. In addition, bi-weekly phone calls will occur with the PI, [name], and [name] (for quality assurance). A Data and Safety Monitoring Board (DSMB) will oversee safety monitoring and will act in an advisory capacity to the NIA Director to monitor participant safety.

Protection Against Study Risks:

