to rise out of? Do they need something to hold onto? What will they use?). Participants will also identify things they should not do, and there will be a discussion on care in case of injury (e.g., call 911 as needed, as they would do in any other incident at home, and be seen by their regular clinical care system for diagnosis, treatment and follow-up. Participants will be instructed on what to report and to whom if they have an adverse event while participating in the workshop). Also, during weekly meetings, participants will report on any situation that arose during their efforts to break up their sitting time (e.g., muscle soreness and/or increases in pain), and then problem solve with input from the health program facilitators (e.g., trying alternative strategies, reducing the number of stands until the soreness subsides, etc). The PI or research assistant will call the health program facilitators on a weekly basis to discuss safety issues & delivery of the intervention, and bi-weekly phone calls will occur with the PI, [name], and [name] (for quality and safety assurance). [name] has an extensive background in falls prevention. She founded and serves as medical director of the multidisciplinary UW-Health Geriatric Falls Clinic. [name] has researched and published extensively on falls prevention and mobility in older adults and is providing falls prevention expertise for this study. {Note: in our previous preliminary research, there were no injuries and pain did not increase even though the majority of the participants reported having arthritis}. When completing the physical function assessments (i.e., balance and chair stand tests), there are minimal risks of falling, muscle soreness, and/or increases in pain. However, to reduce these risks the physical function tests will be conducted near a table or wall in case a participant needs to steady themselves (in case they begin to fall). Also, the assessor will be close enough to the participant to catch them if need be.

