## **DATA COLLECTION AND QUALITY ASSURANCE**

Data Collection: All study data will be collected solely for the research purposes of this study. Outcome assessments consisting of accelerometer, questionnaire and interview data, as well as the Short Physical Performance Battery (i.e., balance, gait speed & chair stands) will be assessed by research assistants from the UW-Madison who are blinded to group assignment (Note: every effort will be made to ensure the assessors remain blinded throughout the duration of the study). The research assistants including the PI ([name]) will travel to the county sites on designated days to collect data at baseline, after the 4-week intervention, and at follow-up (12 weeks). The research assistants will be trained by [name] to complete data assessments prior to data collection. Data collection forms will be standardized and the participant's ID number will be recorded on the forms (rather than their names). Source documents for each participant's data (i.e., participant binder) will be stored in a locked cabinet in [name] laboratory. Data will also be entered (using ID numbers only) by one of the research assistants into an electronic database using SPSS statistical computing environment. The data will be stored in a password protected area with firewall protection. Only designated personnel on the project will have access to the file and password.

Data Management: The UW-Madison is the lead site for this study. [name] will be responsible for data management including activities such as development and maintenance of study materials including a manual of procedures (MOP) and data collection forms; training and supervising research assistants during data collection; overseeing data management via a secure data management system; reviewing data entry for possible errors; and assisting with data analyses. The community partners will not be involved in collecting, storing or analyzing

the data. Their primary responsibilities include recruiting participants, facilitating the *Stand Up and Move More* workshops, and providing information (via a semi-structured interview) about the feasibility of implementing the workshops. The Steering Committee for this study will meet bi-weekly to discuss study progress, data management, and quality control (with additional conference calls as needed).

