**Table 2. Schedule of Assessments**

Assessments	Introductory Meeting	Session 1	Session 2	Session 3	Session 4	Refresher Session 8 wks	Follow-up 12 wks
Informed Consent	X						
Demographic/health questionnaire	X						
SF-36	X				X		X
PROMIS questionnaires	X				X		X
Sedentary Behavior interview	X				X		X
Self-efficacy questionnaire	X				X		X
Self-regulation questionnaire	X				X		X
Outcome expectations questionnaire	X				X		X
Short Physical Performance Battery	X				X		X
Accelerometers	X				X		X
Adverse events			X	X	X	X	X
Fidelity monitoring		X	X	X	X	X	
Satisfaction						X	
Feasibility						X	
Cost estimate							X

Note. Screening of prospective participants and randomization will be completed prior to the introductory meeting.

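### Assessors are declared blinded, but the PI collects outcome data while handling workshop adverse events and calls, so blinding of the SPPB and sitting interview is contradicted for the PI and unprotected for any research assistant who calls facilitators

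*Combined protocol and SAP*

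**What the plan says.** Blinding is stated twice. Research Design and Methods, Measures: "The assessors will be blinded to group assignment". Data Collection and Quality Assurance, Data Collection: the accelerometer, questionnaire, interview and SPPB data "will be assessed by research assistants from the UW-Madison who are blinded to group assignment". Both places promise best efforts to maintain the blind, but neither names a procedure.

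Other text assigns the same people to work on the intervention side:

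- Data Collection, next sentence: "The research assistants including the PI" travel to the county sites to collect data at all three assessments.
- Measures, Sedentary behavior: "Participants will be interviewed by the investigators about their time spent sitting during the day".
- Safety, Adverse Event and Serious Adverse Event Collection and Reporting: "The PI or research assistant will call the health program facilitators on a weekly basis during the workshop to discuss safety concerns". Facilitators collect adverse-event questionnaires at workshop sessions, the PI documents and reports the events, and the PI takes part in bi-weekly calls.
- Safety, Protection Against Study Risks: "The PI or research assistant will call the health program facilitators on a weekly basis to discuss safety issues", and also the delivery of the intervention. The bi-weekly calls are repeated here.
- Participant Confidentiality: the only list linking ID numbers to names is kept in the PI's office.
- Table 2 marks the "Short Physical Performance Battery", the sitting interview, the questionnaires and the accelerometers under Session 4. It has no separate week-4 column, although the 12-week follow-up has one.

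**The concern.** Participants in this trial know their arm, so assessor blinding is the main protection available for measures that a person administers. The SPPB is one of these: a balance test, a timed 4-meter walk and timed chair stands. It is the functional performance measure, and functional performance is a named secondary outcome in Aim 1. The sitting interview, which supplies the analysis by domain (television, reading and so on), is another. An assessor who knows the arm can influence encouragement, timing, balance judgements or prompting without meaning to. If that happened, part of an apparent benefit on these measures could come from the assessment, and the trial would still report the results as blinded.

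**Working it through.** No arithmetic applies. The plan gives no figure for this point, and nothing in it allows the bias to be sized. The check is whether the people named as outcome assessors are also placed where they could learn allocation.

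| Person | Named as collecting outcomes? | Stated contact with allocation information |
|---|---|---|
| PI | Yes, at all three assessments; also the interview, if the PI is one of the investigators meant in Measures | Adverse-event reports from workshops; bi-weekly calls; weekly facilitator calls (shared); ID-name list |
| Research assistant who calls facilitators | Yes | Weekly calls on safety and delivery |
| Research assistant who does not call | Yes | None stated |

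1. *Does a workshop adverse-event report reveal the arm?* Under Wait-List Control Group, controls receive the intervention only after 12 weeks. A report arising at a workshop session before then comes from an intervention participant. Table 2 also marks adverse events at the 12-week follow-up, which both arms attend, so the inference applies to workshop reports only.

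2. *Does the PI see such reports?* Yes. The PI documents adverse events and reports them to the DSMB, IRB and NIA. Data Safety and Monitoring adds that the PI is told of serious events as they occur. ID numbers do not mask identity from the PI, who holds the linking list.

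3. *Does the choice between the PI and a research assistant for the weekly calls protect the blind?* Not as written. Both alternatives are named outcome collectors, and no section says that a caller does not assess.

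4. *Who conducts the interview?* Data Collection places interview data with blinded research assistants. Measures gives the interview to the investigators. These two statements need reconciling.

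5. *Where does week-4 testing take place?* Table 2 puts it under Session 4, which controls do not have at week 4. Measures puts it after the intervention has been delivered, and Data Collection puts it on set days after the 4-week intervention. The table and the text are not aligned.

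6. *Which outcomes are exposed?* Under Analyses, the primary outcomes (total sedentary time, long sitting bouts, sit-to-stand transitions) come from the activPAL, so the person handing out the device has little influence on them. The SPPB and the interview are administered face to face. The routes in steps 1 to 3 open once workshops begin, so they bear on weeks 4 and 12.

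**The case against.** The strongest reply is that the documents show a risk of unblinding and do not show that it occurs. A reader might infer that blinding cannot hold at all. The text does not go that far. The weekly caller may be a research assistant rather than the PI, and nothing says every assistant makes calls. The calls concern safety and delivery, and no section says that individuals are named or attendance discussed. Adverse events are not expected. This stands, and it limits the finding for research assistants to a missing safeguard. It does not remove the contradiction for the PI, who is named as an outcome collector and as the person documenting and reporting adverse events.

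A reader might also infer from Table 2 that the week-4 SPPB is carried out during an intervention workshop. The documents do not establish that. The text places testing after delivery and on set days, and says controls are assessed in the same way as intervention participants, so Session 4 can be read as a label for the week-4 time point. What remains is a labelling ambiguity to clear up.

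A reader might try to size the problem by assuming a bias in standard deviation units and computing a false-positive rate from a two-sample t test. The documents support neither step. They give no bias, and the planned analyses are a 2 x 3 repeated measures ANOVA and longitudinal models with baseline adjustment and a workshop random effect. The pilot gait-speed effect of 0.74 is not a safe yardstick either: the pilot description mentions no control group, so it appears to be a pre-post change.

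Finally, the consequence is narrow. The protocol calls the SPPB objective, the interview is supplementary and answered by participants who know their arm, and the Analyses section already acknowledges that the sample is limited for secondary outcomes. All of this is fair. Assessor blinding cannot remove participants' own reporting bias, and separating roles will not stop a participant from revealing the arm. It does close the leak that the plan itself creates.

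**Conclusion.** The concern holds in limited form. The blinding statements in Measures and Data Collection are contradicted for the PI, and they are unprotected for any research assistant who calls facilitators. For an assistant with no such duties, the text gives no reason to doubt them.

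The exposure covers the SPPB and the sitting interview at weeks 4 and 12. The activPAL primary outcomes, and so the main test of Aim 1, are largely unaffected. The direction and size of any bias cannot be derived from the documents, and none is claimed.

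The conclusion rests on two readings: that a workshop adverse-event report before week 12 identifies an intervention participant, which follows from the wait-list design, and that the PI personally collects outcome data, as Data Collection says. The point should be corrected because the remedy is simple and a named secondary outcome would otherwise carry a blinding claim that the protocol does not support.

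**What to change.** 1. In Data Collection, remove the PI from those who collect outcome data.
2. In both Safety paragraphs that describe the weekly calls, assign the facilitator calls and adverse-event handling to the PI, or to a research assistant who does not assess. State that no one in those roles administers the SPPB or the sitting interview at weeks 4 and 12.
3. In Measures, replace the investigators with the blinded assessors as those who conduct the sitting interview.
4. Reconcile Table 2 with Measures and Data Collection: give the week-4 assessment its own column, separate from Session 4 and applying to both arms.

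If the PI makes the calls and the research assistants assess, no new staff are needed. The documents do not give the number of assistants, so the alternative of a calling assistant who does not assess depends on having enough of them. The cost is less flexibility over who travels on assessment days. In scheduling week 4, the team should also bear in mind that bringing both arms together could let participants discuss the workshop in front of assessors or controls; a separate column does not require the arms to be in the same room.

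If the roles cannot be separated, the protocol and the trial report should not describe the SPPB and interview results as blinded.

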## **PARTICIPANTS RIGHTS AND CONFIDENTIALITY**

IRB Review: This protocol and the informed consent document and any subsequent modifications will be reviewed and approved by the IRB responsible for oversight of the study (UW-Madison Social and Behavioral IRB Committee).

Informed Consent Forms: A signed consent form will be obtained from each participant. The consent form will describe the purpose of the study, the procedures to be followed, the risks and benefits, as well as the voluntary nature of participation and individuals have the right to stop at any time. A signed copy will be given to each participant and this fact will be documented in the participant’s record.

Participant Confidentiality: Participants will be assigned a study ID number upon enrollment into the study and this number will be used in place of the participant’s name on all recording forms. The only list matching the ID number to the participant’s name will be kept locked in the office of the PI ([name]). All computer entry will be done using ID numbers only. Information will not be released without written permission of the participant, except as necessary for monitoring by the IRB and NIA.

Study Discontinuation: The study may be discontinued at any time by the IRB, the NIA, or other government agencies as part of their duties to ensure that research participants are protected.

## **ETHICAL CONSIDERATIONS**

The UW-Madison (and thus this study) is guided by the ethical principles regarding all research involving humans as set forth in the report of the National Commission for the Protection of Human Subjects of Biomedical and Behavioral Research {entitled *Ethical Principles and Guidelines for the Protection of Human Subjects of Research* (the “Belmont Report”)}

## **COMMITTEES**

The Steering Committee for this study includes [name] (PI), [name] (Co-I), and [name] (Community Research Associate). The Steering Committee will be responsible for the overall conduct of the study. Bi-weekly meetings will be held to discuss progress of the study (with additional conference calls as needed).

## **PUBLICATION OF RESEARCH FINDINGS**

Publication of the results of this study will be governed by the policies and procedures developed by the steering committee. Any presentation, abstract, or manuscript will be made available for review by the sponsor prior to submission.

## SUPPLEMENTS

**Table 1. Workshop Sessions Topic Overview**

Group Workshop	Topic/Activities
Session 1	
Introduction and overview of the workshop
 
Record time spent sitting/day (e.g., watching TV, reading, etc)
 
What is sedentary behavior? Information provided on the health consequences of sitting too much
 
Safety discussion: discuss how participants could stand up and move more safely in their environment
 
Modeling (group leader stands and encourages others to stand and move)
 
Goal setting (set a specific manageable goal for the next week, e.g., # of stands and how this will be accomplished)
 
Develop an action plan to meet the goal
 
Discuss self-monitoring (click counter & daily log each night)

Session 2	
Group discussion on why they sit and barriers to standing up
 
Examine goals and behaviors from last week
 
Discuss strategies for trouble-shooting/problem solving
 
Discuss hand-out (strategies used to sit less in a study by Gardiner & colleagues)
 
Modeling (group leader stands and encourages others to stand and move)
 
Set a new goal (specific # of stands/day and how this will be accomplished)
 
Develop an action plan to meet the goal
 
Self-monitoring (discuss self-monitoring during the past week & how to monitor effectively this next week)

Session 3	
Discuss goals and behaviors from previous week
 
Confidence building: share successes/discuss incremental progress
 
Discuss cognitive reframing (how to reframe unhelpful thoughts)
 
Discuss the benefits of standing up and moving more
 
Discuss any problems encountered with problem solving
 
Modeling (group leader stands and encourages others to stand and move)
 
Set a new goal (specific # of stands/day and how this will be accomplished)
 
Develop an action plan to meet the goal
 
Self-monitoring (discuss self-monitoring during the past week & how to monitor effectively this next week)

Session 4	
Record time spent sitting/day (to compare to week 1)
 
Discuss goals and behaviors from previous week
 
Discuss relapsing back into old patterns & how to stay motivated
 
Review benefits of standing up and moving more
 
Discussion of how to stay active in the community
 
Modeling (group leader stands and encourages others to stand and move)
 
Set a new goal (i.e., long-term goal: what to do after this program ends)
 
Develop an action plan to meet the goal
 
Self-monitoring (discuss self-monitoring during the past week & monitoring plans for long-term success)

Refresher Session	
Re-examine motives for sitting less
 
Discuss progress and barriers
 
Share strategies to stand up & move more that worked well
 
Revisit goal with a focus on how to maintain new behaviors over the long-term
 
Modeling (group leader stands and encourages others to stand and move)
 
Congratulate the participants and discuss ongoing activities & social events

